7.4	Patient consent form	40
7.5	Letter to participant GP	51
7.6	Participant personal information questionnaire	52
7.7	MRC breathlessness scale	55
7.8	COPD Assessment Test	56
7.9	PHQ-9	57
7.10	GAD-7	58
7.11	SF-36v2	59
7.12	Service utilisation questionnaire	62
7.13	Checklist to assess the suitability of patient-reported measures	64
7.14	Statistical analysis plan	65
7.15	The Medway Singing and COPD Programme	55

7.16	Interview schedules	68
7.17	Diary for recording of practice of singing at home	71

Lay Summary

Chronic obstructive pulmonary disease (COPD) is a long-term and progressive respiratory disease which negatively affects people's health and wellbeing. The condition deteriorates over time, and there is no cure. However, there is evidence that activities like regular exercise and singing can improve breathlessness and general health and wellbeing.

Previous research has shown positive benefits of singing for respiratory illness, but two recent reviews of the evidence highlights the need for further larger-scale controlled studies with follow-up.

We plan to set up a randomised controlled trial to assess the potential benefits of singing for COPD patients in Medway. A total of 100 patients with moderate to very severe COPD, as assessed by spirometry, will be recruited, assessed and then randomised into two arms of the trial. Half will participate in a singing programme and half will receive usual care. The singing programme will be implemented over 10 ninety minute sessions. The programme will involve breathing exercises and songs which will encourage controlled breathing and progressive extension of the time taken to breathe out.

Participants who are NOT in the singing groups will be offered the opportunity to join a singing group after the final data gathering session.

For all participants, assessments of lung function, breathing patterns and exercise will be gathered before and after ten weeks of weekly singing and then at follow-up after a further three months. Participants will also complete questionnaires about their breathing, quality of life, personal and mental wellbeing and use of medication and health services.

This information will help us assess in a controlled and rigorous way whether singing for people with COPD helps them to manage their breathing difficulties more effectively and contributes to feelings of improved quality of life and wellbeing. It will also enable us to evaluate the potential economic impacts of the initiative for the NHS.

1. Introduction

1.1 Background and rationale

New, innovative initiatives are needed to help people with COPD engage in physical and social activity in order to support independence and quality of life. Recently there has been some interest in the value of singing in promoting wellbeing, including its ability to improve breathing. Currently this is an under-researched, though growing field, and has mixed findings (McNamara et al., 2018). Although surveys have shown that choral singers believe that singing improves their breathing and enhances lung function (Clift & Hancox, 2001; Clift et al, 2009), direct assessment of lung function in professional singers compared with wind and percussion players, has failed to show differences in spirometric parameters (Clift et al, 2008).

Chronic obstructive pulmonary disease (COPD) is an umbrella term that includes a number of specific airway conditions including bronchitis and emphysema. Diagnosis relies on a combination of history, physical examination and spirometry (GOLD, 2017). Dyspnoea (breathlessness) is a cardinal symptom and major cause of disability and anxiety associated with the disease (GOLD, 2017). COPD is associated with other serious health conditions including cardiovascular disease, osteoporosis and depression (Fletcher et al 2010).

Smoking tobacco is the main risk factor for COPD, but other environmental factors can contribute such as exposure to smoke or dust in different occupations, and atmospheric pollution may be important determinants. COPD is progressive over time, especially if individuals continue to smoke or continue to be affected by environmental factors, but individuals may periodically experience episodes of acute worsening of respiratory symptoms or exacerbations, commonly due to infections, or periods of stress.

COPD is a widely prevalent chronic illness throughout the world, and represents a major public health challenge internationally. Gold (2017) states that COPD is currently the fourth leading cause of death in the world but is expected to be the third leading cause of death by 2020. Currently, in the UK, 1.2 million people are estimated to have a diagnosis of COPD (BLF, 2016) which makes COPD the second most common lung disease after asthma. Approximately, 2% of the British population are living with COPD and prevalence increased by 9% between 2008 and 2012.

Currently, 115,000 people are newly diagnosed annually and it is the second biggest cause of death in the UK, with approximately 30,000 deaths due to the condition every year.

COPD makes a big impact on hospital services, and currently accounts annually for over 140,000 hospital admissions and over a million bed days across the UK. This is 1.7% of all hospital admissions and bed days. Exacerbation of COPD is the most common cause of readmissions to hospitals in the UK (Royal College of Physicians, 2017). The direct cost of COPD to the UK National Health Service has been estimated at £810-930 million per year and these costs are expected to rise (DH, 2010). Up to 40% of people with COPD are forced to retire from work prematurely because of the disease (Fletcher et al, 2011).

Since smoking remains the primary cause of COPD, smoking cessation is the intervention with the greatest capacity to influence the natural history of the disease (GOLD, 2017). COPD is not curable, however progress may be slowed down and symptoms reduced through pharmacological management using a stepped approach to inhaled therapies (bronchodilators, steroids and combination therapies), based on the severity of the disease (DH, 2010). In addition, pulmonary rehabilitation can significantly improve exercise capacity, dyspnoea and psychological wellbeing and a minimum of 12 supervised sessions is recommended with patients being encouraged to continue exercise beyond the programme (BTS, 2013).

1.2 Singing and COPD – current state of evidence

Research specific to singing and COPD can be divided into:

- controlled trials
- quantitative studies without controls; and
- qualitative studies (mostly reflecting participant perceptions recorded via written comments or interviews and focus group discussions).

In addition, a number of reviews of related literature exist.

Controlled trials

Four controlled trials have been identified (see Table 1), three of which are randomised. All reported interventions of 1 hour either weekly or twice weekly and duration ranged from 6 weeks to 24 weeks. Participant numbers were limited to 13-15 in the intervention groups and equal or fewer numbers in controls. Two of the studies involved the control groups engaging in alternative group

work, the remaining two involved usual care. A variety of measures were used in these studies, making comparisons difficult, however, both of the Lord et al (2010,2012) studies reported a significant increase in physical wellbeing assessed by the SF-36.

Quantitative studies without controls

Studies without controls (Table 2) are predominantly single cohort studies with pulmonary function and other measures taken at baseline, endpoint and often midpoint. Numbers of participants completing range from 7 to 228. With the exception of an early study (Engen 2005), these studies tend to run for longer than the controlled trials above. Only one study, which had both long term follow-up and a large cohort (Morrison et al 2013) showed significant improvement in pulmonary function. A reduction in anxiety was demonstrated in two studies and there was further support for the need for large controlled trials.

Qualitative studies

A number of studies included embedded qualitative evaluations (Table 3) through either inviting written comments on questionnaires or (more commonly) through conducting interviews. Numbers interviewed vary between 5 and 37, however responses are almost universally favourable and themes are common across studies.

Reviews

Four reviews which included singing for people with COPD have been conducted between 2015 and 2018, though only one (McNamara et al.'s Cochrane Review) focused solely on this group and was limited to randomised controlled trials (Table 4). All these reviews commented on the limited or conflicting evidence for the impact of singing on respiratory function. Where evidence does exist the quality is low due to small sample numbers and other features such as attrition rates.

Gick & Nicol (2015) conducted a review of singing for respiratory health, including studies pertaining to COPD. Those considered are Engen (2015), Morrison et al. (2013), Lord et al. (2010, 2012), Goodridge et al. (2013) and Bonilha et al. (2009). They raise a number of challenges in conducting such studies, including: attrition; length of intervention; conducting non-medical interventions for medical conditions (and therefore working in partnership with health professionals); and the finite length of the intervention (and what happens when the research ends). They conclude that the results from the studies reviewed suggest promising but inconclusive findings overall.

Lewis et al (2016) conclude their review with a consensus statement covering seven statements on the current status of knowledge together with pointers for research and practice:

- Singing for Lung health has the potential to deliver benefits for respiratory conditions.
- Qualitative data is strongly positive.
- Small trials have been positive but evidence for functional status and economic evaluation is needed.
- A distinction needs to be made between singing specifically for lung health and more generic community singing groups.
- There is a need to define competencies and training pathways for group facilitators.
- Appropriate outcome measures need to be identified which are meaningful to participants. CAT is one such possible measure.
- There is a need for robustly designed and powered trials before singing for lung health can be recommended for routine management of conditions.

Daykin et al (2016) found only two studies met their criteria in looking at wellbeing outcomes where singing was compared to a comparator or where a qualitative study was undertaken, focusing on COPD. Evidence pointed to outcomes including reduced stress and improved wellbeing but was of a low quality.

McNamara et al (2018) used the Cochrane guidelines and templates for a review of RCTs only (being the highest quality evidence) and only three studies met the criteria with limited opportunity for meta-analysis. A number of omissions and limitations in the reporting of studies were noted including the recording of compliance with home practice, which facilitators in all three studies requested.

1.3 Psychological and social impacts of COPD

In addition to the physical consequences associated with lung damage, people with COPD are at heightened risk of additional threats to their wellbeing and health, including social isolation, anxiety and depression. In some cases, the mental health consequences can be clinically significant and prompt further intervention.

In the current study a measure of mental health related quality of life and clinical measures of generalised anxiety disorder and depression will be used as secondary outcome measures to assess the extent to which singing as an intervention is beneficial for the mental health and wellbeing of people with COPD.

1.4 Structured Light Plethysmography

The relevance of measuring tidal breathing to detect differences between those with respiratory diseases such as Chronic Obstructive Pulmonary Disease (COPD) and healthy subjects has been well established (Cain and Otis, 1949; Kostianev, Hristova and Lluhev, 1999; Yamauchi et al., 2012; Yamada et al., 2017). There are a number of approaches to measuring tidal breathing including respiratory inductance plethysmography and optoelectronic plethysmography (Mehra and Strohl, 2009). The current more common method used is pneumotachography (PNT) which is considered gold standard (Iles et al., 2015). PNT however, involves COPD patients wearing a mouthpiece potentially causing unease which may change the patients' respiratory pattern leading to inaccurate results (Laveneziana et al., 2015). Consequently, the need for a technique with minimal patient cooperation and high levels of accuracy is present.

Structured Light Plethysmography (SLP) is a relatively new non-contact technique which measures tidal breathing requiring minimal patient cooperation (de Boer, 2010). Subjects have a light grid projected onto their chest and two cameras record the movement of the thoraco-abdominal (TA) wall allowing tidal breathing parameters to be calculated (Alimohamed, 2011; Motamedi-Fakhr, Wilson and Iles, 2016b). Respiratory rate, which is a tidal breathing parameter derived from SLP, has been validated against the gold standard clinician over-scored capnography (Motamedi-Fakhr, Wilson and Iles, 2016b). Iles et al. (2015) and Motamedi-Fakhr et al. (2017) tested the accuracy and repeatability of SLP against PNT, concluding SLP to be of equal gold standard. This research provides promising results for SLP to be introduced as a non-invasive method for measuring tidal breathing.

The use of SLP as a clinical tool to measure tidal breathing specifically among COPD patients has been evaluated (Motamedi-Fakhr, Wilson and Iles, 2016; Nierat et al., 2017). Motamedi-Fakhr, Wilson and Iles (2016) used thirty-one COPD patients and thirty-one healthy subjects to investigate whether SLP can recognise differences in tidal breathing. The results show that SLP does recognise differences between the two groups and that it may also have potential as a method to

detect COPD. These results compliment the findings from Nierat's et al. (2017) research which used thirty COPD and thirty healthy subjects, differences in breathing patterns were observed. SLP also provides more precise measurements of TA movements which allow for a greater analysis (Nierat et al., 2017). Conclusive observations highlight SLP as an appropriate method to assess tidal breathing among COPD patients, both Motamedi-Fakhr, Wilson and Iles (2016) and Nierat et al. (2017) empathise the need for more research.

SLP may also have potential use in measuring the effectiveness of COPD treatments (Laveneziana et al., 2014; Hmeidi et al., 2016; Hmeidi et al., 2017). Laveneziana et al. (2014) tested sixteen COPD patients before and after bronchodilators (BD), SLP showed differences in some of the tidal breathing parameters highlighting a response to BD. Although not among COPD patients, Hmeidi et al. (2016) and Hmeidi et al. (2017) conducted research using thirty children with asthma and thirty without, SLP showed breathing differences between the two groups and observed a positive response to BD. These results show promise for health professionals to use SLP as a tool to measure the effectiveness of COPD treatments.

1.5 Feasibility studies in Medway

Singing for Better Breathing

As a basis for assessing the feasibility of setting up and running a randomised controlled trial in Medway and in association with Medway Community Healthcare Respiratory Team, two 'singing for better breathing' groups were established in Medway in May, 2017. Participants were recruited through visits to pulmonary rehabilitation classes (PR) run by the respiratory team in two community venues. Members of the De Haan Centre spoke about the idea of 'singing for better breathing' and ran taster exercises. Interest levels were high with approximately half of PR participants expressing a willingness to participate in singing groups. Two groups were set up in Gillingham and St. Mary's Island, and of the people expressing interests at PR, approximately half were able to join one of the groups (i.e. 25% of those contacted initially). This suggests that in recruitment for a further study, at least four times the required sample would need to be reached through direct contact.

The two groups ran weekly over three months, and participants were guided through a structured progressive programme of exercises and singing in line with the approach adopted in previous

studies conducted by the De Haan Centre. In addition, participants were given a printed resource and access to video of exercises and singing to support individual practice at home between sessions.

The singing programme was evaluated by [name] as part of her PhD research within the De Haan Centre, and three measures were employed in a simple baseline-follow up design: the COPD Assessment Test (CAT), the Asthma Control Questionnaire (ACQ) and the Warwick Edinburgh Mental Wellbeing Scale (WEMWBS). The table below gives the means on these questionnaires at baseline and after the programme, and show clearly that significant improvements took place on the CAT and WEMWBS with a marginally significant improvement on the Asthma Control Questionnaire.

Scale	Sample	Baseline	Follow-up	t	p
CAT	21	25	20	2.75	0.01
WEMWBS	21	49	55	-2.61	<0.02
ACQ	20	12	10	2.01	<0.10

The results from the CAT questionnaire were especially encouraging, as the improvement of five points on the scale is clearly greater than the established 'minimal clinically important' change score of two points (Kon et al., 2014).

A film based on the project also supports the findings from the questionnaires, with participants giving positive testimonies of the positive benefits they experienced from regular singing. See: <https://vimeo.com/245825761> (Password s4bbMedway).

Trial of Structured Light Plethysmography

As we propose to make use of Structured Light Plethysmography to assess potential changes in breathing patterns as a result of singing, a trial of the technique was also undertaken with volunteers from the Medway Singing for Better Breathing group. As a comparison, members of the Rochester Choral Society were also invited to participate to provide a comparison with people with healthy lungs in April, 2018. In the course of the assessment participants were asked to sing a short extract from *My Bonnie Lies over the Ocean* and also a simple counting song (I can sing to one, two, three etc. up to 8, then to 12, then to 16). The songs were used to assess the potential value of examining breathing patterns during singing, especially when the demands on the out-

breath increase as the numbers counted in the second song increase. This worked well, but on reflection for the trial, it was clear that a simple assessment of breathing at rest, and an assessment of breathing following a period of structured exercise, would be easier to undertake and of greater relevance to the aims of the trial.

A film of the assessments together with testimonies from participants with COPD and those with healthy lungs can be viewed here:

<https://www.youtube.com/watch?v=P1KJYPWm2Hs&feature=youtu.be>

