1.7 Public and patient involvement

Considerable care has been taken in the design of the current study to consult with patients affected by COPD and interested members of the public (including family members of people with COPD), drawing on participants of singing for better breathing groups previously established by the De Haan Centre and which have continued to meet. A member of the research team has a diagnosis of COPD. In addition, people with COPD and other members of the lay public were formally invited to review the protocol in the course of its development. The Trial Management Committee will also include patients affected by COPD and lay members.

Table 1. Research with controls

Reference	Number of participants (intervention vs control)	Intervention	Control	Measures	Findings	Conclusions
Bonilha et al 2009	Randomised 15:15	1 hr weekly singing for 24 weeks. Relaxation, respiratory & vocal exercises then Brazilian folks songs. Enc home practice	Handcraft work 1 hour weekly over 24 weeks. Relaxation exercises. Including home practice	Pulmonary function, SGRQ, QoL and Borg scale	Intervention group showed small improvement in maximal expiratory pressure, control group declined. Both groups increased their scores on SGRQ	Regular singing may improve QoL and improve maximal expiratory pressure. Additional studies recommended to define role of singing as potential to assist PR
Lord et al 2010	Randomised 15:13	1 hr sessions for 6 weeks of twice weekly singing.	Usual care	SF36, HADS, single breath counting, breath hold, walk test	Significant improvements in anxiety (HADS) and physical component of SF36 in intervention group	Singing classes can improve QoL and anxiety but did not improve measures of breath control or functional capacity. Further work needed to quantify magnitude and duration of improvement
Lord et al 2012	Randomised 13:11	1 hr sessions twice weekly for 8 weeks. Includes vocal exercises, posture and relaxation training. Homework CD.	Weekly Film club for 8 weeks followed by group discussion	HADS, CAT, SF36, walk test, Borg scale, single breath holding	Significant improvements in the physical component of SF36 in intervention group.	Participation in singing lessons may be a useful activity for people with COPD

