- The Medway feasibility study (see above) showed an improvement on the CAT questionnaire of five points, more than twice the minimum clinical difference score of two. A change of five points represents a moderate effect size of approximately 0.5. If such a difference arises between the intervention and control groups in the proposed trial, where data is paired from pre-test and follow up, a sample size of 40 per group will be more than sufficient to give 90% power at a p-value of 5% (two-tailed) (Chan, 2003).
-
- The proposed study will assess participants immediately following the intervention and then after a further three months. No such follow-up has taken place in previous trials.

- The current study is a pilot and if the findings are encouraging the results could be subsumed into a larger multi-centre trial conducted in the same way.

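### Section 2.2 defends 40 per group with a five-point CAT change that is uncontrolled, imprecise (95% CI 1.2 to 8.8) and measured at programme end, not an arm difference at six months

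*Protocol*

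**What the plan says.** Section 1.5 reports a feasibility study of two singing groups in which "three measures were employed in a simple baseline-follow up design". There was no control group. The table row for the COPD Assessment Test reads "CAT 21 25 20 2.75 0.01" (sample, baseline mean, follow-up mean, t, p). No SD or interval is given. The text concludes that "the improvement of five points on the scale is clearly greater than the established 'minimal clinically important' change score of two points".

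Section 2.2 says the sample size was set by resources without a formal power calculation, and raises the ethics of an under-powered trial. Among the considerations offered in reply it states that "A change of five points represents a moderate effect size of approximately 0.5". It continues "If such a difference arises between the intervention and control groups in the proposed trial", and concludes that 40 per group would be more than enough for 90% power at a two-sided 5% level.

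Three other places bear on this:
- Section 1.6 puts the primary end point at six months post-baseline.
- Section 2.1 names two CAT points as an important criterion for judging the trial clinically.
- Appendix 7.14 expects the condition effect at T3 to be significant but smaller than at T2. It gives d=.68 as the smallest effect detectable with 80% power and 40 per group.

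**The concern.** The five points are the only CAT magnitude offered in support of 40 per group. They are used as if they were a settled quantity and the same quantity that the trial will estimate.

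Neither holds. The estimate comes from 21 people and its own test statistic implies a wide interval. It is a change within one group, so anything that would have moved CAT scores without singing is included in it. It was also taken at the end of the programme, whereas the primary comparison comes about three months later.

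At stake is how the primary result will be read. If the true arm difference is two or three points, a non-significant result is likely. Set against an expectation of five points, it could be reported as no worthwhile benefit. Conversely, if the reasoning of 1.5 were repeated, a point estimate above two with a wide interval could be reported as plainly exceeding the threshold.

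**Working it through.** **Inputs.** From 1.5: n = 21, means 25 and 20, t = 2.75, p = 0.01. From 1.5 and 2.1: threshold of 2 points. From 2.2: 40 per arm, two-sided 5%, five points taken as d of about 0.5. From Appendix 7.14: d=.68 at 80% power. Assumed: a CAT SD of 8.3 to 10, because the protocol states none (origin in step 5).

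**1. Reproduce the printed p value.** Paired t test, df = 20: p = 2 × P(T₂₀ > 2.75) = 0.012, which rounds to the printed 0.01. The other two rows of the table also fit a paired test (WEMWBS 0.017, printed <0.02; ACQ 0.059, printed <0.10).

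**2. Interval for the change.** SE = 5 / 2.75 = 1.818. With t(0.975, 20) = 2.086, the 95% CI is 5 ± 2.086 × 1.818 = 5 ± 3.79, or 1.21 to 8.79.

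**3. Change against two points.** t = (5 − 2) / 1.818 = 1.65; two-sided p = 0.115, one-sided p = 0.057.

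**4. Sensitivity.** The means are printed as whole numbers, so the true difference could lie between 4 and 6. Holding t at 2.75, the lower limit runs from 0.97 to 1.45 and the two-sided p against two points from 0.18 to 0.08. An unpaired reading (df = 40) gives a lower limit of 1.33, and a normal quantile gives 1.44. The lower limit is below two in every variant.

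**5. What 40 per arm can detect, in CAT points.** The SD of change in the feasibility data is 1.818 × √21 = 8.33. The SD implied by equating five points with d = 0.5 is 5 / 0.5 = 10. These two values form the assumed range.
- Protocol's d=.68, shown beside rows marked as Bonferroni-corrected: 0.68 × 8.33 = 5.7; 0.68 × 10 = 6.8.
- Two-sample t test at an unadjusted 5%, detectable d = 0.634: 0.634 × 8.33 = 5.3; 0.634 × 10 = 6.3.

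I take .68 as printed. A two-sample test gives 0.634 at 5% and 0.737 at 5%/3, so it lies between them.

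**6. Power with 40 per arm, two-sided 5%, unadjusted (noncentral t).**

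| True arm difference | SD 8.3 | SD 10 |
|---|---|---|
| 2 points | 19% | 14% |
| 3 points | 36% | 26% |
| 4 points | 56% | 42% |

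**7. What each quantity measures.**

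| | Feasibility five points (1.5) | Primary comparison (1.6, 2.5) |
|---|---|---|
| Contrast | Change within one group | Difference between randomised arms |
| Comparator | None | Usual treatment following rehabilitation |
| Time | End of a three-month programme | Six months post-baseline |
| Expected size (Appendix 7.14) | – | T3 effect smaller than T2 |

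The two differ in contrast, comparator and time. On the protocol's own expectation, even a genuine end-of-programme effect should not be carried unchanged to six months.

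**The case against.** **The statement in 1.5 is true of the estimate.** Five exceeds two, and the protocol claims no test against two. This stands. The fault is limited to the word *clearly*, in a background section that openly describes the design.

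**The five points did not set the sample size.** Section 2.2 says resources did, its use of five points is conditional, and the study is called a pilot. A reader might infer that the trial was sized on five points, or that the protocol declares five points to be its expected arm difference. The documents support neither. The conditional sentence is nonetheless the argument offered for 40 being enough, in direct reply to the ethical question the section raises.

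**Rehabilitation may not have contributed.** Section 1.5 says that "Participants were recruited through visits to pulmonary rehabilitation classes (PR) run by the respiratory team in two community venues", and 1.1 says that "pulmonary rehabilitation can significantly improve exercise capacity, dyspnoea and psychological wellbeing". A reader might infer that part of the five points is a rehabilitation effect. The documents do not say when the baseline CAT fell relative to rehabilitation, so this is conjecture. The point needs only the absence of a control group.

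**Other CAT evidence.** Table 1 has one randomised trial that lists CAT and reports significance only on the SF-36 physical component. A reader might infer that singing had no CAT effect there. The row gives no CAT estimate and the trial randomised 13:11, so its silence shows nothing about size. Table 2 lists an evaluation with a significant CAT improvement, but it is uncontrolled, only 47% had COPD, and no magnitude is given. Neither supplies a substitute figure.

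**The detectable effect is already stated.** It is, as d=.68 in Appendix 7.14, but not in CAT points and not in 2.2, where sufficiency is argued.

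**The power figures rest on assumptions.** They do: an assumed SD and an unadjusted two-arm comparison, not the planned mixed ANOVA. Baseline adjustment could raise power, but the protocol gives no correlation. Whether d = 0.5 yields 90% power with 40 per arm is a separate question; this point would stand even if it did.

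**Conclusion.** The concern holds in a limited form. Section 2.2 supports 40 per group with a before-after change in 21 people whose 95% CI, 1.2 to 8.8, includes values below the two-point threshold. That change does not estimate an arm difference at the six-month primary end point. The interval rests on the printed t and n and a paired test, which the printed p values fit; rounding does not alter the conclusion.

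On an assumed SD of 8.3 to 10, 40 per arm can detect about 5.7 to 6.8 points using the protocol's d=.68, or 5.3 to 6.3 unadjusted. Power for a true two-point difference is about 14% to 19% unadjusted.

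It does not follow that the five-point estimate is wrong, that singing has no CAT effect, or that the trial should not run at this size. The wording in 1.5 is minor on its own. The sufficiency statement in 2.2 and the reading of the primary result are worth changing.

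**What to change.** 1. **Section 2.2.** Describe the five points as an uncontrolled, imprecise end-of-programme estimate (95% CI 1.2 to 8.8). Replace the claim that 40 per group is ample with what 40 per arm can detect: the protocol's d=.68 at 80% power, about 5.7 to 6.8 CAT points if the SD is 8.3 to 10, with the SD labelled as an assumption. If the unadjusted 5.3 to 6.3 is also given, say that the multiplicity correction explains the difference from Appendix 7.14. State that unadjusted power for a true two-point difference is about 14% to 19%.
2. **Sections 2.1 or 2.8.** State that the T3 arm difference in CAT will be reported with a 95% CI and read against the two-point criterion. A non-significant result is then not taken as no worthwhile benefit, and a point estimate above two is not taken as clearly exceeding it.
3. **Section 1.5 (minor).** Give the interval and drop *clearly*.

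Do not add a statement about the CAT result of the Table 1 trial, since its row gives no estimate.

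The cost is wording only, with no extra patients, data or change of analysis. The downside is a less favourable stated justification for the sample size.
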